12. LONG-TERM SAFETY ANALYSES

Protocol: TNX-CY-P306 Page 25 of 36

Final v1.0

Select safety analyses will be conducted on the data collected across Studies TNX-CY-P301, TNX-CY-P303, and TNX-CY-P306 (the "long-term analysis period"). For purposes of clarity, only subjects in the TNX-CY-P306 Safety Population are included in these analyses, except where specified in Section 12.1. The purpose of this set of analyses is to support the long-term safety profile of TNX-102 SL 5.6 mg per day. Certain definitions and analyses in this Section 12 may differ from that of other sections in this SAP.

All analyses will be summarized for the TNX-102 SL group only, except where specified in Section 12.1. For subjects who were treated with placebo in Study TNX-CY-P301, analyses will exclude the subject data from Study TNX-CY-P301 (except to the extent the baseline record may come from Study TNX-CY-P301, as applicable). For purposes of Sections 12.3 and 12.4, baseline is the last assessment prior to dosing with TNX-102 SL for the first time.

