## 7.2. Inclusion Criteria

- 1. The patient has either a) completed the double-blind lead-in study and completed or is active (at the time of study discontinuation) in the 12-week open-label extension study (P303), or b) is currently enrolled in the double-blind lead-in study that was discontinued due to results of an interim analysis, and is judged by the investigator as reasonably compliant, with at least 60% compliance with study medication usage (based on drug accountability).
- 2. The patient has provided written informed consent to participate in this extension study. *Note:* Separate written, signed informed consent will be required if the patient is to participate in the optional pharmacogenomic assessment. A decision not to participate in the optional pharmacogenomic testing will not affect the patient's eligibility for the main study.
- 3. The patient met all prior inclusion and exclusion requirements for the double-blind leadin study, or the site received medical monitor approval for the patient to remain in the lead-in study after the retrospective discovery of an entry violation that did not pose any threat to the patient's safety or well-being.
- 4. During the course of the lead-in study or 12-week open-label extension study, the patient has had no intervening medical conditions including pregnancy, clinically significant increase in suicidal ideation (plan or intent) or significant worsening of depression, newly arising clinically significant abnormal laboratory tests, or any clinically significant, uncontrolled, or unstable medical or surgical condition that could affect the patient's ability to participate in the study or potentially compromise the patient's well-being during the study.
- 5. The patient does not require treatment with a potent (strong) cytochrome P450 subtype 3A4 (CYP3A4) inhibitor, or St. John's wort.
- 6. The patient is willing to refrain from use of all other formulations of cyclobenzaprine for the duration of the study.
- 7. The patient is willing to refrain from use of monoamine oxidase inhibitors for the duration of the study.
- 8. Female patients of childbearing potential continue to agree to practice one of the medically acceptable methods of birth control detailed in the lead-in study.

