6. ANALYSIS POPULATIONS

The following analysis populations are planned for this study:

• Safety Population (SAFETY): All participants who receive at least 1 dose of study drug in Study TNX-CY-P306. Participants who are issued study drug, but return 100% of it (i.e., none consumed) will be excluded from the Safety Population; likewise, participants that have no follow up following receipt of study drug to indicate they took drug are excluded. All analyses will be performed using this population, unless otherwise specified in this SAP.

Protocol: TNX-CY-P306 Page 14 of 36

Final v1.0

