12.1 Long-Term Disposition

The numbers and percentage of subjects who received study drug in each study, completed each study, and withdrew from each study will be tabulated, by treatment sequence and overall. The number and percentage of subjects in each unique study sequence will also be tabulated. This summary will be created once for the TNX-CY-P301 Safety Population (ie, any subject who dosed in TNX-CY-P301) and repeated for the TNX-CY-P306 Safety Population (ie, any subject who dosed in TNX-CY-P306).

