12.2 Long-Term Adverse Events Analyses

For purposes of the long-term AE analyses, treatment-emergent AEs (TEAEs) are any AE with an onset at the time of or following the start of treatment in any of the 3 studies (TNX-CY-P301, TNX-CY-P303, and TNX-CY-P306). To align with the study-level CSR, any AE identified as a TEAE in the study-level CSR for study TNX-CY-P301 will be deemed a TEAE.

Analyses of TEAEs will be presented only for the TNX-102 SL group. Specifically, for subjects who were actually treated with placebo in Study TNX-CY-P301, any TEAEs collected in Study TNX-CY-P301 would be disregarded; only TEAEs that are newly-emergent in Studies TNX-CY-P303 or TNX-CY-P306 would be included. For subjects treated with TNX-102 SL in Study TNX-CY-P301, any AE identified in either the TNX-CY-P303 or TNX-CY-P306 database will be deemed treatment-emergent and eligible for inclusion in analyses, unless the start date is collected and is prior to the treatment start date in TNX-CY-P301.

An overall summary of AEs will summarize the number and percentage of subjects with any TEAE, nonfatal serious TEAE, TEAE leading to death, TEAE by maximum severity, TEAE by maximum relationship, TEAE leading to dose interruption, TEAE leading to dose reduction, TEAE leading to study drug discontinuation, or oral cavity TEAE (see definition below in this section) by category, in the long-term analysis period.

The following analyses of TEAEs will be completed:

Overall summary of TEAEs

Protocol: TNX-CY-P306 Page 26 of 36

Final v1.0

- Incidence of TEAEs by SOC and preferred term
- Incidence of serious TEAEs by SOC and preferred term
- Incidence of TEAEs leading to study drug discontinuation by SOC and preferred term
- Incidence of oral cavity TEAEs by category and preferred term
- Incidence of serious oral cavity TEAEs by category and preferred term
- Incidence of oral cavity TEAEs leading to study drug discontinuation by category and preferred term
- Incidence of TEAEs potentially suggestive of abuse by SOC and preferred term

Oral cavity TEAEs are defined in Section 10.1. TEAEs are identified as potentially suggestive of abuse based on the preferred terms listed in Appendix 3. Of note, somnolence and sedation are known and expected cyclobenzaprine drug effects; these preferred terms will still be included in these displays, if present.

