In addition, the incidence of patients with each category of oral cavity TEAEs will be summarized by increments based on the relative start day of the AE compared to first dose of active drug in any study (0-12 weeks, >12-24 weeks, >24-36 weeks, >36-48 weeks, and >48 weeks). Intervals may be changed for more meaningful interpretation based on the actual distribution of the AE data. For each increment, the denominator will be the number of subjects with risk-time extending into that time interval, specifically, with a duration of exposure to TNX-102 SL of at least the lower limit of that increment. For instance, the number of subjects with >12 weeks of exposure would be the denominator for the >12-24 week increment. Duration of exposure is defined in Section 12.5). The last dose date is the last dose date in Study TNX-CY-P306, and the first dose date is the first dose of TNX-102 SL in any study. If a subject experienced more than one TEAE in a given category, the first event will be selected.

A similar analysis will be provided for the incidence of TEAEs and serious TEAEs by SOC and preferred term.

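### The pooled long-term safety tables omit everyone who stopped TNX-102 SL or died before P306, so the discontinuation and fatal TEAE incidences are biased low

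*SAP*

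**What the plan says.** SAP Section 12 opens: "Select safety analyses will be conducted on the data collected across Studies TNX-CY-P301, TNX-CY-P303, and TNX-CY-P306". Its aim is stated plainly: "The purpose of this set of analyses is to support the long-term safety profile of TNX-102 SL 5.6 mg per day". The population is narrower than the data span: "only subjects in the TNX-CY-P306 Safety Population are included in these analyses, except where specified in Section 12.1". SAP Section 6 defines that population as "All participants who receive at least 1 dose of study drug in Study TNX-CY-P306".

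The clock does not start at P306. In SAP 12.2 the interval tables place an event by its start day "compared to first dose of active drug in any study", and the duration of exposure in 12.2 and 12.5 runs from the first TNX-102 SL dose in any study. The pooled outputs in 12.2 include "Incidence of TEAEs leading to study drug discontinuation by SOC and preferred term", the same for oral cavity events, and TEAEs leading to death. SAP 12.4 adds laboratory shifts and liver-test categories over the same span.

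The one exception is disposition in SAP 12.1: "This summary will be created once for the TNX-CY-P301 Safety Population", then repeated for the P306 Safety Population.

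Protocol 7.2 sets the conditions for entering P306. The patient must have completed P301 and completed or be active in P303, or be currently enrolled in P301. Compliance of at least 60% is required. Criterion 4 rules out, among other things, increased suicidality, significant worsening of depression and "newly arising clinically significant abnormal laboratory tests".

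**The concern.** Follow-up begins before the event that qualifies a patient for inclusion. For anyone exposed to TNX-102 SL in P301 or P303, the period before P306 is immortal with respect to leaving treatment: only patients who stayed long enough to enter P306 are counted.

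Discontinuation for an adverse event is a central tolerability measure for a chronic bedtime treatment, and oral cavity discontinuations matter particularly for a sublingual tablet. If early failures on drug are removed by the choice of population, a table that appears to give cumulative incidence from the first dose does not do so. The SAP plans no Section 12 AE or laboratory analysis in all TNX-102 SL recipients, and attaches no caveat to the tables.

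**Working it through.** **1. The plan's own exposure figure.** Protocol 6.1 and SAP 3 give a maximum continuous exposure of about 64 weeks. P301, P303 and P306 Track A last 12 + 12 + 40 = 64 weeks, so the figure reproduces. For such a patient 24/64 = 37.5% of the counted time lies before P306.

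**2. Which outputs are affected, without assuming any rate.**

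| Output | Effect of admitting only patients dosed in P306 |
|---|---|
| TEAEs leading to discontinuation, overall and oral cavity (12.2) | No discontinuation that took place in P301 or P303; biased low |
| TEAEs leading to death (12.2) | No death in P301 or P303; biased low |
| TEAE interval rows, 0-12 and >12-24 weeks (12.2) | On-drug events from P301/P303 are counted, but only in patients who met P306 entry criteria |
| TEAE rows beyond about 24 weeks | Little affected: patients who left before P306 had at most about 24 weeks on drug, so would not be in these denominators |
| Laboratory shifts and liver categories (12.4) | Entry criterion 4 selects against new abnormalities, incompletely: Protocol 10.1 says final-visit results arrive after entry |
| Crude any-TEAE percentage; vital signs (12.3) | Selected, but direction not established |

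The discontinuation row assumes that stopping drug for an adverse event ended participation in P301 or P303. The documents do not give those studies' rules.

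**3. Size for discontinuation, illustration only.** The one documented input is N = 200, the enrolment ceiling. The assumed inputs are:
- f, the share of P306 patients exposed before P306: 0.5 to 1.0
- s, the share of earlier TNX-102 SL starters who reach P306: 0.5 to 0.9
- a, the share of non-continuers who stopped for an AE: 0.1 to 0.3
- q, AE discontinuation within P306: 0.05

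Omitted starters: L = fN/s - fN. Section 12 reports q. With all starters the crude figure is (qN + aL)/(N + L).

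- Low end (f = 0.5, s = 0.9, a = 0.1): L = 11; (10 + 1.1)/211.1 = 5.3%.
- Middle (f = 0.75, s = 0.7, a = 0.3): L = 64; (10 + 19.3)/264.3 = 11.1%.
- High end (f = 1, s = 0.5, a = 0.3): L = 200; (10 + 60)/400 = 17.5%.

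All compare with 5.0% under Section 12. The pre-P306 component is essentially 0% under Section 12, against a(1 - s) = 1% to 15% of previously exposed starters.

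**4. Direction for TEAEs generally, illustration only.** Assume 100 continuers with 64 weeks' exposure, 43 omitted patients with 4 weeks, and a constant hazard giving a 20% first-event risk over 12 weeks: h = -ln(0.8)/12 = 0.0186 per week. Let the omitted patients' hazard be k times h.

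| k | 0-12 week rate, all starters relative to Section 12 set | 0-12 week crude %, Section 12 set to all | Any-time crude %, Section 12 set to all |
|---|---|---|---|
| 1 | 1.000 | 20.0 to 16.1 | 69.6 to 50.8 |
| 2 | 1.129 | 20.0 to 18.1 | 69.6 to 52.8 |
| 4 | 1.365 | 20.0 to 21.7 | 69.6 to 56.4 |

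The exposure-adjusted early rate rises if omitted patients had a higher event hazard and is unchanged if they did not. Crude percentages can fall when short-exposure patients are added, so crude tables alone would not show the selection reliably.

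**The case against.** The restriction is stated openly. SAP 12.1 shows withdrawals for everyone dosed in P301, P301 has its own study report, and SAP 10.1.1 reports P306 discontinuations separately. All true, and the attrition is partly visible. But disposition carries no adverse event or laboratory results, and a separate report does not correct pooled tables that start the clock in P301.

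Three stronger readings are tempting, and the documents do not support them.

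- *A reader might infer that the early interval rows are structurally free of events, or describe only patients who tolerated the drug.* SAP 12.2 plans interval tables for oral cavity TEAEs, TEAEs and serious TEAEs, not for discontinuations, and it counts on-drug events from P301 and P303. P301-placebo patients who enter P306 directly take their first TNX-102 SL dose there, so their early events and discontinuations are captured. Patients still active in P301 on drug, or in P303, when those studies stopped may have part of their early exposure observed in P306.
- *A reader might infer that the whole long-term profile is biased favourably.* Rows beyond about 24 weeks are little affected, and these carry much of the Protocol's aim of at least 52 weeks' exposure.
- *A reader might compound assumed per-study rates into a fixed multiple.* Rates of 3/2/3%, 5/3/5% and 10/5/5% give 1 - (1-a)(1-b)(1-c) = 7.8%, 12.5% and 18.8%, where a, b and c here are the P301, P303 and P306 rates. Against 3.0%, 5.0% and 5.0%, that is a factor of 2.5 to 3.8. It requires every patient to be on drug throughout and everyone without an AE discontinuation to roll over. With 60% rollover at each step, a + 0.6(1-a)b + 0.36(1-a)(1-b)c gives 5.2%, 8.4% and 14.2%, a factor of 1.7 to 2.8 before any placebo patients are added. No single multiple is defensible.

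**Conclusion.** The point holds in a bounded form. Among patients exposed before P306, the pooled incidences of TEAEs leading to discontinuation (overall and oral cavity) and of TEAEs leading to death omit those outcomes from P301 and P303 and are biased low. This follows from the population definition and the entry criteria, given the participation assumption in the working for discontinuations. Exposure-adjusted TEAE rates for the first 24 weeks and laboratory abnormalities are probably too favourable, if patients who left early had more events than those who continued. For crude any-TEAE percentages and for vital signs the direction is open.

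The size cannot be computed: the documents give no P301 or P303 discontinuation rates, no rollover fractions and no mix of entry routes. Under the assumed ranges it runs from slight (5.3% against 5.0%) to several-fold (17.5% against 5.0%). The change should be made because these tables are meant to support the long-term safety profile.

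**What to change.** Repeat the 12.2 adverse event tables and the 12.4 laboratory tables, with 12.5 exposure, for all patients who received at least one dose of TNX-102 SL in P301, P303 or P306. Keep the existing rule that drops P301 data for placebo patients. Report exposure-adjusted rates beside crude percentages, since the added patients have short exposure. Take the cumulative discontinuation, fatal-TEAE and early-interval results from this set.

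Keep the current P306-only tables, but state in their titles or footnotes that they are conditional on entry to P306 and omit patients who stopped TNX-102 SL earlier.

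Starting risk time at P306 entry is not a good substitute: it would discard adverse events observed on drug in P301 and P303 and would largely duplicate Section 10.

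The cost is additional programming and output. The 12.1 disposition run does not supply what is needed: adverse event, laboratory and exposure records are required for all earlier TNX-102 SL recipients. Trial conduct does not change. The sponsor should expect a probably less favourable discontinuation figure.

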12.1 Long-Term Disposition

The numbers and percentage of subjects who received study drug in each study, completed each study, and withdrew from each study will be tabulated, by treatment sequence and overall. The number and percentage of subjects in each unique study sequence will also be tabulated. This summary will be created once for the TNX-CY-P301 Safety Population (ie, any subject who dosed in TNX-CY-P301) and repeated for the TNX-CY-P306 Safety Population (ie, any subject who dosed in TNX-CY-P306).

12.2 Long-Term Adverse Events Analyses

For purposes of the long-term AE analyses, treatment-emergent AEs (TEAEs) are any AE with an onset at the time of or following the start of treatment in any of the 3 studies (TNX-CY-P301, TNX-CY-P303, and TNX-CY-P306). To align with the study-level CSR, any AE identified as a TEAE in the study-level CSR for study TNX-CY-P301 will be deemed a TEAE.

Analyses of TEAEs will be presented only for the TNX-102 SL group. Specifically, for subjects who were actually treated with placebo in Study TNX-CY-P301, any TEAEs collected in Study TNX-CY-P301 would be disregarded; only TEAEs that are newly-emergent in Studies TNX-CY-P303 or TNX-CY-P306 would be included. For subjects treated with TNX-102 SL in Study TNX-CY-P301, any AE identified in either the TNX-CY-P303 or TNX-CY-P306 database will be deemed treatment-emergent and eligible for inclusion in analyses, unless the start date is collected and is prior to the treatment start date in TNX-CY-P301.

An overall summary of AEs will summarize the number and percentage of subjects with any TEAE, nonfatal serious TEAE, TEAE leading to death, TEAE by maximum severity, TEAE by maximum relationship, TEAE leading to dose interruption, TEAE leading to dose reduction, TEAE leading to study drug discontinuation, or oral cavity TEAE (see definition below in this section) by category, in the long-term analysis period.

The following analyses of TEAEs will be completed:

Overall summary of TEAEs

Protocol: TNX-CY-P306 Page 26 of 36

Final v1.0

- Incidence of TEAEs by SOC and preferred term
- Incidence of serious TEAEs by SOC and preferred term
- Incidence of TEAEs leading to study drug discontinuation by SOC and preferred term
- Incidence of oral cavity TEAEs by category and preferred term
- Incidence of serious oral cavity TEAEs by category and preferred term
- Incidence of oral cavity TEAEs leading to study drug discontinuation by category and preferred term
- Incidence of TEAEs potentially suggestive of abuse by SOC and preferred term

Oral cavity TEAEs are defined in Section 10.1. TEAEs are identified as potentially suggestive of abuse based on the preferred terms listed in Appendix 3. Of note, somnolence and sedation are known and expected cyclobenzaprine drug effects; these preferred terms will still be included in these displays, if present.

In addition, the incidence of patients with each category of oral cavity TEAEs will be summarized by increments based on the relative start day of the AE compared to first dose of active drug in any study (0-12 weeks, >12-24 weeks, >24-36 weeks, >36-48 weeks, and >48 weeks). Intervals may be changed for more meaningful interpretation based on the actual distribution of the AE data. For each increment, the denominator will be the number of subjects with risk-time extending into that time interval, specifically, with a duration of exposure to TNX-102 SL of at least the lower limit of that increment. For instance, the number of subjects with >12 weeks of exposure would be the denominator for the >12-24 week increment. Duration of exposure is defined in Section 12.5). The last dose date is the last dose date in Study TNX-CY-P306, and the first dose date is the first dose of TNX-102 SL in any study. If a subject experienced more than one TEAE in a given category, the first event will be selected.

A similar analysis will be provided for the incidence of TEAEs and serious TEAEs by SOC and preferred term.

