## 9.6. Early Termination (ET)

In accordance with the Declaration of Helsinki, patients have the right to withdraw from the study at any time for any reason, and they will be advised of this right. The investigator and Tonix also have the right to remove patients from the study. Specific reasons for removal of a patient from the study could include, but are not limited to:

- An AE
- An illness that, in the judgment of the investigator or Tonix, might invalidate the study results or place the patient at risk
- The request of the patient, investigator, or Tonix, whether for administrative or other reasons
- Pregnancy

Patients who wish to terminate their participation in the study should be instructed to come to the clinic for an Early Termination Visit. The purpose of the Early Termination visit is to obtain critical information about the patient's participation, and should be scheduled preferably before there has been a substantial lapse in study medication usage. However, even if there has been a medication lapse, the patient should be encouraged to return to the clinic for this visit, and should be instructed to return all remaining study medication.

The following assessments and procedures are completed at this visit in the following general order:

- Collect returned study medication from patient and perform drug accountability
- Assess study drug compliance
- Assess for occurrence of AEs

- Assess for changes in concomitant medications
- Obtain vital signs including weight
- Draw blood for clinical laboratory tests
- For women of child-bearing potential, conduct urine pregnancy test
- Inspect the oral cavity and document findings, if any
- Have the patient complete the PROMIS-Sleep Disturbance Scale and SDS
- Have the patient complete the BDI-II
- Conduct the C-SSRS after reviewing the results of the BDI-II
- Conduct CGI-I comparing to the P306 baseline

Once these assessments have been completed, the patient may be discharged from the study, provided there is no need for additional follow-up to continue to monitor an AE or other condition.

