## 11.3. Serious Adverse Events (SAEs) and Serious Adverse Drug Reactions

Any SAE that occurs at any time during the study, or within 28 days after the patient's last exposure to study drug, including a clinically significantly abnormal laboratory test result that is considered serious, must be reported to Tonix or its designee(s) so that Tonix may comply with regulatory obligations. If the SAE is life-threatening or fatal, it must be reported to Tonix or its designee(s) immediately, by email or telephone. For these and all other SAEs, an SAE report form must be completed and sent by facsimile or email to Tonix or its designee(s) within 24 hours of the site's initial awareness of the event. These requirements apply equally to all patients, regardless of the study phase or the at-risk patient's treatment assignment.

A serious adverse event (experience) or reaction is any untoward medical occurrence that, at any dose:

- Results in death,
- Is life-threatening,
- Requires in-patient hospitalization or prolongation of existing hospitalization,
- Results in persistent or significant disability/incapacity,
- Is a congenital anomaly/birth defect, or
- Is an important medical event

*NOTE:* The term "life-threatening" in the definition of "serious" refers to an event in which the patient was at risk of death at the time of the event. It does not refer to an event that hypothetically might have caused death if it were more severe.

Medical and scientific judgment should be exercised in deciding whether expedited reporting is appropriate in other situations, such as important medical events that may not be immediately life-threatening or result in death or hospitalization but may jeopardize the patient or may require intervention to prevent one of the other outcomes listed in the definition above. *These should also usually be considered serious*. Examples of such events are intensive treatment in an emergency room or at home for allergic bronchospasm, blood dyscrasias or convulsions that do not result in hospitalization, or development of drug dependency or drug abuse.

A death occurring during the study or reported to the Investigator after study participation (no required post-study time limit) must be reported to Tonix or its designee(s) immediately, whether or not it is considered treatment-related. Initial SAE reports must be followed by detailed

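### In the SAP 12.2 interval tables, an adverse event that starts after the last dose can enter a numerator whose denominator excludes the patient

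*SAP*

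**What the plan says.** **Numerator.** SAP 12.2 defines a long-term TEAE as "any AE with an onset at the time of or following the start of treatment in any of the 3 studies". That is a start bound with no end bound. Events go into intervals "based on the relative start day of the AE compared to first dose of active drug in any study", and the intervals are "0-12 weeks, >12-24 weeks, >24-36 weeks, >36-48 weeks, and >48 weeks". Only the first event in a category is used.

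**Denominator.** For each interval it is the number of patients "with a duration of exposure to TNX-102 SL of at least the lower limit of that increment". The SAP's own example is that "the number of subjects with >12 weeks of exposure would be the denominator for the >12-24 week increment". Exposure is last dose minus first dose plus 1 (SAP 12.5). For its end, 12.2 states: "The last dose date is the last dose date in Study TNX-CY-P306". No post-dose window is added.

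**Scope.** The rule is written for oral cavity TEAEs and extended to all TEAEs and serious TEAEs by SOC and preferred term.

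**Collection after the last dose.** Protocol 11.3 requires reporting of SAEs that occur "within 28 days after the patient's last exposure to study drug", and of deaths with no time limit. Protocol 9.6 assesses AEs at the early termination visit and says that "even if there has been a medication lapse, the patient should be encouraged to return to the clinic for this visit".

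**The concern.** The numerator runs on time since first dose, with no end. The denominator runs on exposure and ends at the last dose. If an event starts after the last dose and on the far side of an interval boundary, the patient is counted above the line and not below it. The result is not a proportion of the patients at risk.

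These tables are meant to show whether risk changes with longer exposure, and long-term safety is the primary objective. Serious TEAEs are the most exposed, because they alone have a defined period of collection after treatment. Split by SOC and preferred term, their counts may be low enough for one such patient to show. Without a rule, two programmers could also treat the same event differently.

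**Working it through.** The plan attaches no figure to this analysis, so there is nothing to reproduce. The check applies the two rules as written.

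**1. Example patients.** Days are counted from the first TNX-102 SL dose. Boundaries are at 12 × 7 = 84, 168, 252 and 336 days.

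| Last dose (= exposure, days) | AE onset day | Numerator interval | Lower limit (days) | In that denominator? |
|---|---|---|---|---|
| 80 | 82 | 0-12 weeks | 0 | yes |
| 80 | 90 | >12-24 weeks | 84 | no (80 < 84) |
| 160 | 180 | >24-36 weeks | 168 | no (160 < 168) |
| 330 | 350 | >48 weeks | 336 | no (330 < 336) |
| 365 | 380 | >48 weeks | 336 | yes |

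The mismatch needs an onset after the last dose and a boundary between the two. The Day 160 case could be a patient on placebo in P301 who entered P306 directly and stopped in Week 23.

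**2. Share of post-treatment events that cross a boundary.** Assume the stop day is uniform within an 84-day interval. A delay of x days (x ≤ 84) then crosses with probability x/84. For a delay uniform over 0 to 28 days, the mean is 14, so the share is 14/84 = 16.7%.

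**3. Effect of one such patient.** The denominators are assumed: 1/50 = 2.0 points, 1/100 = 1.0 point, 1/200 = 0.5 point. The last is the planned maximum enrolment.

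**4. Expected number of such patients.** A simplified simulation used 200 patients (the planned maximum), all starting active drug at Day 0 and followed to Day 365. All other inputs were assumptions:
- dropout of 30% or 50%, uniform over the year;
- a 5% chance of a first event per 12 weeks on drug;
- a 28-day post-treatment window;
- a post-treatment hazard of 1 or 3 times the on-drug hazard.

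The mean number of numerator patients outside their denominator was 0 in the first interval and about 0.03 to 0.18 in each later one. The change in the interval percentage ran from 0.027/144.6 = 0.02 points to 0.159/108.1 = 0.15 points.

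**5. Does an end bound cure it?** Suppose onset must be on or before the last dose, and onset falls beyond lower limit L. Then exposure ≥ onset day > L, so the patient is in the denominator. This also holds for a patient with exactly 84 days of exposure, where the SAP's rule (at least the limit) and its example (more than 12 weeks) differ.

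**The case against.** The strongest reply is that the effect is close to nil and the tables are descriptive, with no test or decision rule attached. Much of that stands:

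- Few patients can be affected. Section 12 is limited to the P306 Safety Population, except for disposition in 12.1. Track A patients who completed P303 enter P306 with about 24 weeks of active drug. Completers on either track reach about 52 weeks or more and are already in the >48 week denominator.
- Collection of non-serious AEs largely ends at the early termination visit. Patients are then discharged (protocol 9.6) and followed only for an ongoing AE or other condition (SAP 7.1).
- Where the first event in a category occurred on drug, a later off-drug event in that category does not enter.
- No event is lost. Every TEAE still appears in the overall tables.

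It can also be said that SAP 12.2 speaks of risk time reaching into the interval, which suggests a matched risk set was intended. But the same sentence then narrows risk time specifically to duration of exposure, and the worked example does the same. The wording shows the aim and does not deliver it.

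The convention in SAP 11.2 for a missing last dose date (the day before the last attended visit) does not settle the matter. It can close the gap for AEs reported at that visit and open one for an SAE reported later. The SAP does not say whether it carries into 12.5.

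**Conclusion.** The rule is wrong as written, and nothing in either document closes the gap. The likely numerical effect is small. The 17% is a share of post-treatment events, not of all events, and rests on the two uniformity assumptions. The 1.0 and 2.0 point figures are what one mismatched patient does, not a forecast that one will occur. Under the assumed rates in step 4, fewer than 0.2 such patients are expected per later interval.

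A reader might infer more than the documents support:

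- *That half of post-treatment events cross a boundary.* This needs delays of up to 12 weeks (42/84 = 50%). No such lapse is stated, and protocol 9.6 prefers the early termination visit before a substantial lapse in dosing.
- *That the problem centres on patients who stop because of an AE.* The AE that causes stopping normally starts on drug and is correctly matched. The documents give no reasons or rates for stopping.
- *That events are put in the wrong interval.* On the SAP's axis of time since first dose, a Day 180 event belongs in >24-36 weeks. Only denominator membership is inconsistent, and it invites the reader to see the event as arising under exposure the patient did not have.

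**What to change.** In SAP 12.2, state that a TEAE is counted in an interval only if its onset is on or before the last TNX-102 SL dose. By step 5, every numerator patient is then in that interval's denominator. Report events with later onset on a separate post-treatment line in each table.

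If a post-dose window is wanted for serious TEAEs, use the 28 days of protocol 11.3 in that table only. Count onsets up to last dose plus 28 days, and include in the denominator patients whose exposure plus 28 days reaches the lower limit. Do not extend this to the oral cavity or all-TEAE tables. Non-serious AEs are not systematically collected for 28 days after the last dose. On the uniform stop-day assumption, 28/84 = 33% of patients who stop within an interval would join the next denominator without matching collection, which would dilute the incidence.

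The cost is a few sentences in the SAP and a small change to the programs for all three sets of interval tables. A few events move to the post-treatment line. No new data are needed.
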